#### **6.5.5. Clinical Laboratory Assessments**

The following clinical laboratory tests will be evaluated by a central laboratory. Specific instructions for transaminase elevations are provided in Section 5.2.4. For any other unexplained clinically relevant abnormal laboratory test occurring after study drug administration, the test should be repeated and followed up at the discretion of the Investigator, or as per DMC advice, until it has returned to the normal range or stabilized, and/or a diagnosis is made to adequately explain the abnormality. Additional safety laboratories and assessments as indicated by the clinical situation may be requested. Clinical laboratory assessments are listed in [Table 6](#) and will be assessed as specified in the Schedule of Assessments ([Table 1](#)).

While local laboratory results may be used for urgent clinical decisions, on the day of the assessments, all laboratory assessments specified in [Table 6](#) that are performed at the clinic should also be sent in parallel to the central laboratory. In the case of discrepant local and central laboratory results on samples drawn on the same day, central laboratory results will be relied upon for clinical decisions.

Clinical laboratory assessments may be collected at the clinical study center or at home by a trained healthcare professional. In patients randomized to receive olmesartan as the protocol-specified background antihypertensive medication, blood samples for RAAS biomarkers should be collected in the morning and in the seated/upright position (after blood pressure measurements and before any assessments collected in the supine position). Blood samples for laboratory evaluation should be collected after the completion of blood pressure assessments.

Spot urine collections for albumin and creatinine should be obtained in the morning.

For any safety event or laboratory abnormality, additional laboratory assessments, imaging, and consultation may be performed for clinical evaluation and/or in consultation with the Medical Monitor; results may be collected and should be included in the clinical database.

**Table 6: Clinical Laboratory Assessments**

Hematology	
Complete blood count with differential	
Serum Chemistry	
Sodium	Potassium
BUN	Phosphate
Uric acid	Albumin
Total protein	Calcium
Glucose	Bicarbonate
Creatinine and eGFR	Chloride
Creatinine clearance (screening only)	
Liver Function Tests	
AST	ALP
ALT	Bilirubin (total and direct)
GGT	
Urinalysis	
Visual inspection for appearance and color	Bilirubin
pH (dipstick)	Nitrite
Specific gravity	RBCs
Ketones	Urobilinogen
Protein	Leukocyte esterase
Glucose	Microscopy (if clinically indicated)
Coagulation	
Prothrombin time	International normalized ratio
Partial thromboplastin time	
Fasting Lipid Panel and Glycemic Assessments (see Section 6.5.5.1)	
Lipid panel, including HDL-C, non-HDL-C, LDL-C, apolipoprotein A1, triglycerides, total cholesterol	Insulin
Fasting plasma glucose	HbA1c
Immunogenicity (see Section 6.5.5.2)	
ADA	
Pregnancy Testing/FSH Screening (see Section 6.5.5.3)	
$\beta$ -human chorionic gonadotropin (females of child-bearing potential only)	Follicle-stimulating hormone (postmenopausal women only)

Abbreviations: ADA=anti-drug antibodies; ALP=alkaline phosphatase; ALT=alanine aminotransferase; AST=aspartate aminotransferase; BUN=blood urea nitrogen; eGFR=estimated glomerular filtration rate; FSH=follicle-stimulating hormone; GGT=gamma glutamyl transferase; HbA1c=hemoglobin A1c; HDL-C=high-density lipoprotein; LDL-C=low-density lipoprotein; RBCs=red blood cells.

#### **6.5.5.1. Fasting Lipid Panel and Glycemic Assessments**

Blood samples for fasting plasma glucose, insulin, lipid panel (including total cholesterol, high-density lipoprotein [HDL-C], non-HDL-C, low-density lipoprotein, apolipoprotein A1, and triglycerides), and HbA1c will be collected at the time points listed in the Schedule of Assessments ([Table 1](#)). Patients are required to fast for  $\geq 10$  hours before sample collection for fasting glucose, insulin, lipid panel, and HbA1c. Samples should be collected at approximately the same time of day ( $\pm 2$  hours).

#### **6.5.5.2. Immunogenicity**

Blood samples will be collected to evaluate anti-drug antibodies (ADA). Blood samples for ADA testing must be collected before study drug administration (on days when study drug is to be dosed) or at a time point corresponding to the time of study drug dosing (on other days) as specified in the Schedule of Assessments ([Table 1](#)). A blood sample to evaluate ADA will be collected at the ET visit, if applicable. Blood samples for ADA will be analyzed at a regulated bioanalytical laboratory.

Details regarding the processing, shipping, and analysis of the samples will be provided in the Laboratory Manual.

#### **6.5.5.3. Pregnancy Testing**

A pregnancy test will be performed for females of child-bearing potential. A serum pregnancy test will be performed at screening, and urine pregnancy tests will be performed thereafter per the Schedule of Assessments and any time pregnancy is suspected. More frequent pregnancy testing may be performed where required per local requirements. The results of the pregnancy test must be known before study drug administration. Patients who are pregnant at screening are not eligible for study participation. Any woman with a positive urine pregnancy test, subsequently confirmed by a positive serum pregnancy test, during the study will be discontinued from study drug but will continue to be followed for safety. Patients who become pregnant while on study will be followed at least until the pregnancy outcome is known (see Section [6.5.6.7](#) for follow-up instructions).

A blood sample will be drawn at screening to measure the levels of follicle stimulating hormone in order to confirm postmenopausal status in all women suspected to be postmenopausal (see Section [5.11.1](#) for definition of postmenopausal state).

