#### 4.3.1. Discontinuation of Study Drug or Declining Procedural Assessments

Reasons for discontinuation of study drug include any of the following:

- Significant protocol deviation; which includes required treatment with prohibited medication (as defined in Section 5.9.1) per Investigator discretion
- AE
- Non-adherence to treatment regimen
- Pregnancy
- Lost to follow-up
- Other reason (non-AE)
- Or, study is terminated by the Sponsor

If possible, the Investigator will confer with the Sponsor or Medical Monitor before discontinuing dosing in the patient. Patients who are pregnant will be discontinued from study drug dosing immediately (see Section 6.5.6.7 for reporting and follow-up of pregnancy). A positive urine pregnancy test should be confirmed by a serum pregnancy test prior to discontinuing the study drug.

Patients who discontinue study drug and/or decline procedural assessments should not be automatically removed from study. In general, patients who discontinue study drug dosing for any reason will be encouraged to remain on the study to complete the remaining assessments so that their experience is captured in the final analyses.

If this occurs, the Investigator is to discuss with the patient the appropriate processes for discontinuation from study drug and must discuss with the patient the options for continuation of the Schedule of Assessments (Table 1), including different options for follow-up and collection of data (eg, in person, by phone, by mail, through family or friends, or from options not involving patient contact, such as communication with other treating physicians or from review of medical records), including endpoints and AEs, and must document this decision in the patient's medical records.

If a patient has an AE, including SAEs, and/or laboratory abnormalities that in the judgment of the investigator, taking into account the patient's overall status, requires interruption or discontinuation from treatment with study drug, the event should be followed as described in Section 6.5.6. When a patient discontinues study drug dosing, the primary reason must be recorded in the eCRF. Patients who discontinue study drug and remain on study may receive treatment consistent with local standard practice for their disease per Investigator judgement, as applicable.

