Patients who discontinue from study drug during the 6-month DB period (defined as the time the first dose of study drug is administered on Study Day 1 through completion of the Month 6 assessments) will be encouraged to remain on the study and complete assessments (excluding pharmacokinetic [PK] assessments) through Month 6. They will also be asked to complete Safety Follow-up visits once every 6 months after the last dose of study drug per the safety follow-up schedule (see [Table 1](#)) until PD recovery or 12 months after the last dose of study drug (whichever is earlier); see Section [3.1](#).

Patients who discontinue study drug during the OLE period will be asked to return for their next scheduled visit to complete EOT/ET assessments and complete Safety Follow-up visits once every 6 months after the last dose of study drug per the safety follow-up schedule (see [Table 1](#)) until PD recovery or 12 months after the last dose of study drug (whichever is earlier); see Section [3.1](#).

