### **5.11. Other Requirements**

#### **5.11.1. Contraception**

Females of child-bearing potential must be willing to use a highly effective method of contraception from 14 days before the first dose of protocol-specified background antihypertensive medication, throughout study participation, and through safety follow-up (if applicable; see Section 3.1).

Birth control methods which are considered highly effective include:

- Placement of an intrauterine device.
- Placement of an intrauterine hormone-releasing system.
- Bilateral tubal occlusion.
- Surgical sterilization of male partner (with the appropriate post-vasectomy documentation of the absence of sperm in the ejaculate; for female patients on the study, the vasectomized male partner should be the sole partner for that patient).
- Established use of oral (except low-dose gestagens), implantable, injectable, or transdermal hormonal methods of contraception associated with the inhibition of ovulation.
- True sexual abstinence, when in line with the preferred and usual lifestyle of the patient. Periodic abstinence (eg, calendar, ovulation, symptothermal, post-ovulation methods) and withdrawal are not acceptable methods of contraception. Abstinent patients must agree to use one of the above-mentioned contraceptive methods if they start heterosexual relationships during the study and through safety follow-up (if applicable; see Section 3.1)

Investigators should advise females of childbearing potential of the most appropriate birth control method available within their country taking into account local medical practice.

Females of child-bearing potential include female patients who have experienced menarche (or begin menarche over the course of the study), and who are not postmenopausal or permanently sterilized (eg, bilateral oophorectomy, hysterectomy, or bilateral salpingectomy). A postmenopausal state is defined as the absence of menses for 12 months without an alternative medical cause, confirmed by follicle stimulating hormone level within the postmenopausal range.

For male patients, no contraception is required. However, use by males of contraception (condom) may be required in some countries, eg, France, in order to comply with local requirements as described in the corresponding patient ICFs.

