#### **6.5.6.7. Pregnancy Reporting**

If a female patient becomes pregnant during the study through safety follow-up (see Section 3.1), the Investigator must report the pregnancy to the Sponsor or designee within 24 hours of being notified of the pregnancy. Details of the pregnancy will be recorded on the pregnancy reporting form. The patient should receive any necessary counseling regarding the risks of continuing the pregnancy, the possible effects on the fetus, and be counseled to not breastfeed for 90 days after the last dose of study drug.

The pregnancy should be followed by the Investigator until completion. At the completion of the pregnancy, the Investigator will document the outcome of the pregnancy. If the outcome of the pregnancy results in a postpartum complication, spontaneous abortion, stillbirth, neonatal death, or congenital anomaly, then the Investigator should follow the procedures for reporting an SAE as outlined in Section 6.5.6.4.

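### For a pregnancy confirmed after Day 1 of the double-blind period, the mandatory stop covers only study drug, of which no dose remains; no pregnancy rule directs what happens to the daily background antihypertensive

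*Protocol*

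**What the plan says.** **The pregnancy rules.** Section 4.3.1: "Patients who are pregnant will be discontinued from study drug dosing immediately". Section 6.5.5.3: after a positive urine test confirmed in serum, the woman "during the study will be discontinued from study drug but will continue to be followed for safety".

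**What the term covers.** Section 6.5.6.2 separates study drug (zilebesiran or placebo) from the background antihypertensive and uses study treatment for both. Under Section 5.2.2 study drug in the double-blind period is one injection on Day 1. Section 3.1 states that under Amendment 3 there is no Month 6 dose.

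**The background drug.** Section 5.3 has all patients continue it through Month 6. The grounds given there for reducing or holding it are low blood pressure, intercurrent illness and volume depletion.

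**What else applies.**
- Section 4.3.1: "Patients who discontinue study drug and remain on study may receive treatment consistent with local standard practice for their disease per Investigator judgement". It also says "If possible, the Investigator will confer with the Sponsor or Medical Monitor before discontinuing dosing in the patient". Patients who stop study drug in the double-blind period "will be encouraged to remain on the study and complete assessments (excluding pharmacokinetic [PK] assessments) through Month 6".
- Section 6.5.6.7: "the Investigator must report the pregnancy to the Sponsor or designee within 24 hours of being notified of the pregnancy". The patient is to be counseled on "the possible effects on the fetus, and be counseled to not breastfeed for 90 days after the last dose of study drug".
- Section 5.11.1 requires contraception "from 14 days before the first dose of protocol-specified background antihypertensive medication, throughout study participation".
- Section 1.3 commits to dosing the background agents per local labeling. Section 5.3 refers sites to the Pharmacy Manual for prescribing information.

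**The concern.** The one compulsory drug action in pregnancy is aimed at a product that has already been given in full. The product still being taken daily falls under a general rule of continuation, with no pregnancy exception written into it. The protocol itself links background exposure to pregnancy, because the contraception requirement is timed from the first background dose and not from the injection.

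What is at stake is patient safety and consistent conduct. One site may continue the background drug, another stop it, and a third switch it, with or without replacement treatment, and each can point to protocol text in support. Estimation of the treatment effect is not at stake.

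**Working it through.** The plan gives no figure on this point to reproduce. The check sets the provisions side by side and then counts doses and days.

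**Step 1. Study-drug doses left to withhold after Day 1.** Planned doses in the double-blind period: 1, on Day 1 (5.2.2). Dose at Month 6 under Amendment 3: 0 (3.1). Doses remaining after Day 1: 0. The study-drug stop still has two effects. It puts the patient on the follow-up path for discontinued patients, and it opens the local-practice clause in 4.3.1. It prevents no further exposure.

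**Step 2. Does any rule act on the background drug?**

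| Situation | Section | Background drug addressed? |
|---|---|---|
| Low blood pressure | 5.3, 5.8.1 | Yes, downtitrate or interrupt |
| Intercurrent illness, volume depletion | 5.3 | Yes, may be held |
| Renal dysfunction | 5.8.3 | Yes, oral antihypertensives named |
| Hyperkalemia | Table 5 | Yes, olmesartan named |
| Pregnancy | 4.3.1, 6.5.5.3, 6.5.6.7 | No |

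Elsewhere, then, the protocol says so when it wants the oral drugs reconsidered. In 6.5.6.7 the only drug-specific advice, on breastfeeding, is again tied to study drug.

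**Step 3. Which period is affected?** Run-in and Day 1 are covered: pregnancy is exclusion 27, eligibility is checked at each randomization (3.4), and the test result must be known before dosing (Table 1, footnote b). After Month 6 the background drug ends. The interval is therefore after Day 1 and up to Month 6.

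**Step 4. How long can that interval be?** Nominal Month 6 is Day 169 (Table 1). Days remaining = 169 − day of confirmation.

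| Confirmed on | Days to Day 169 |
|---|---|
| Day 15 | 169 − 15 = 154 |
| Day 29 | 169 − 29 = 140 |
| Day 57 | 169 − 57 = 112 |
| Day 85 | 169 − 85 = 84 |
| Day 113 | 169 − 113 = 56 |
| Day 141 | 169 − 141 = 28 |

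Confirmation must fall after Day 1, so the figure is always below 169 − 1 = 168. The Month 6 visit window adds up to 7 days (Day 15: 154 + 7 = 161). Visit days serve only as reference points, since 6.5.5.3 also requires a test whenever pregnancy is suspected.

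**Step 5. How many patients?** Only women of child-bearing potential among about 630 planned (300 olmesartan, 210 amlodipine, 120 indapamide). Neither their number nor a pregnancy rate is given. Highly effective contraception is required and women planning pregnancy are excluded, so few cases are expected.

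**The case against.** The strongest reply is that nothing here is false or contradictory. The local-practice clause in 4.3.1 is specific to patients who have stopped study drug, so it can be read as overriding the general regimen in 5.3. The labeling sentence in 1.3 is worded as a commitment, and the protocol applies local labeling in practice when it sets the olmesartan dose. The Pharmacy Manual, which is not shown, may cover use in pregnancy. Every case reaches the Sponsor within 24 hours, and the fetal-effects counseling is not limited to study drug.

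Most of this stands. A reader might infer that the protocol obliges a pregnant patient to keep taking her background drug. It does not: stopping is allowed, and these safeguards would probably prompt it. A reader might also take the day counts as expected exposure. They are only the length of the interval without a directive, and nothing in the document suggests that a known pregnant patient would be kept on the drug to Month 6.

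What does not fall away is that these provisions permit or refer elsewhere. None of those visible joins pregnancy to an action on the background drug, while the two rules that do name pregnancy act on a drug with no dose left.

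**Conclusion.** The point holds as a minor patient-safety correction. After Day 1 the compulsory pregnancy action withholds 0 doses. The daily background drug continues by default for up to, but less than, 168 further days (up to 7 more with the visit window), and pregnancy is not a listed ground for holding it. Cases should be few, and the primary and secondary endpoints and their analysis are unaffected.

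The conclusion assumes that study drug carries its 6.5.6.2 meaning in the pregnancy rules, and that Amendment 3 applies to the patient.

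A reader might go further and conclude that olmesartan in particular must be stopped. The protocol gives no pregnancy data for any of the three agents, so that step has to come from the local labels. The contraception timing in 5.11.1 shows that background exposure was considered in relation to pregnancy; it does not establish the risk of any one drug.

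**What to change.** Keep the study-drug stop. Add to Sections 4.3.1 and 6.5.5.3 a rule to this effect: on confirmed pregnancy, the background antihypertensive and any escape antihypertensive are reviewed immediately with the Medical Monitor and are stopped or switched wherever local labeling does not support use in pregnancy, with replacement antihypertensive treatment per local standard practice. Escape drugs belong in the rule because Table 4 allows a CCB or a thiazide-type diuretic to be added before Month 6. In Section 5.3, make continuation through Month 6 subject to this rule. The sponsor sets the drug-specific steps, including those for olmesartan, from the local labels that Section 1.3 already invokes.

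The cost is a few sentences in two sections, one clause in a third, and a site notification. No visit, procedure, endpoint or analysis is added. The downside is that the few affected patients leave their assigned background regimen. They entered with a 24-hour mean SBP of 130 to 160 mmHg on that drug, so they need a managed switch, and their later blood pressure values will be off the cohort's regimen.

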#### **6.5.5.4. Additional Liver Function Assessments**

Additional laboratory assessments will be performed in patients who experience any LFT abnormalities as outlined in Section [5.2.4](#). Following the occurrence of elevated liver transaminases or other LFT abnormalities per central laboratory, all assessments in [Table 7](#) will be performed 1 time, as well as hematology, serum chemistry, LFT, and coagulation assessments from [Table 6](#), and other assessments or evaluations per Investigator discretion, as appropriate.

Monitoring, including criteria for dose modification or withholding the study drug, is described in Section [5.2.4](#).

**Table 7: Hepatic Assessments in Patients Who Experience Elevated Transaminases**

Extended Hepatic Panel	
HBsAg, HBC antibody IgM	Parvovirus B19 DNA - quantitative
HAV antibody IgM	HHV-6 DNA viral load - quantitative
HCV antibody	Anti-nuclear antibodies
HCV RNA PCR – quantitative	Anti-smooth muscle antibodies
HEV antibody IgM	Anti-LKM1 antibody
Herpes Simplex Virus 1 and 2 antibody IgM, IgG	Anti-mitochondrial antibodies
Herpes Zoster Virus IgM, IgG	Anti-SLA
Epstein-Barr Virus antibodies, IgM and IgG	Ferritin
Cytomegalovirus antibodies, IgM, IgG	Ceruloplasmin
Imaging	
Abdominal ultrasound with Doppler flow (or CT or MRI) including right upper quadrant	
Focused Medical and Travel History	
Use of any potentially hepatotoxic concomitant medications, including over the counter medications and herbal remedies	Alcohol consumption and drugs of abuse
Other potentially hepatotoxic agents including any work-related exposures	Recent travels to areas where hepatitis A or E is endemic

Abbreviations: CT=computed tomography; DNA=deoxyribonucleic acid; HAV=hepatitis A virus; HBC=hepatitis B core; HBsAg=hepatitis B virus surface antigen; HCV=hepatitis C virus; HEV=hepatitis E virus; HHV-6=human herpesvirus 6; IgG=immunoglobulin G antibody; IgM=immunoglobulin M antibody; LKM1=liver/kidney microsome-1 antibody MRI=magnetic resonance imagery; PCR=polymerase chain reaction; RNA=ribonucleic acid; SLA=soluble liver antigen

Note:

- All laboratory assessments will be measured in a central laboratory. The full panel of assessments should only be performed once; individual assessments may be repeated, as needed.

## 6.5.6. Adverse Events

### 6.5.6.1. Definitions

#### Adverse Event

According to the ICH E2A guideline Definitions and Standards for Expedited Reporting, and 21 Code of Federal Regulations 312.32, IND Safety Reporting, an AE is any untoward medical occurrence in a patient or clinical investigational subject administered a medicinal product and which does not necessarily have a causal relationship with this treatment.

